**$H_0: \pi_i \geq 0.16$  (50% of reference rate = 32%)**

**$H_A: \pi_i < 0.16$**

In this formulation,  $\pi_i$  is the true malalignment probability for the investigational device.

A one-sided type 1 error of  $\alpha=0.05$  was assumed. Using industry standard software (nQuery Advisor 7.0, Module POT0x-1), it was determined that statistical power to reject the null hypothesis in favor of the alternative hypothesis is equal to 89.3% with a sample size of N=103

### **THINK Surgical, Inc.**

Proprietary rights of THINK Surgical, Inc. are involved in the subject matter of this material. It is submitted in confidence for a specific purpose and the recipient by accepting this material agrees that it will not be used other than for the express purpose for which it was delivered.

Disclosure to others without written permission from THINK Surgical, Inc. is forbidden.

patients if the true malalignment rate is 0.07. The power for this test remains above 80% as long as the sample size is 95 patients or larger.

#### Continued Access Arm

There will be no formal hypothesis testing with the Continued Access Arm of the study. Patients will mainly be followed for safety and to gain additional information on device use, therefore, no power analysis has been performed to estimate sample size. The Continued Access Arm will enroll up to 50 patients.

### **9.3. Analysis Plan**

Demographic, baseline, peri-operative and postoperative characteristics for all recruited cases (both study arms) will be assessed from data which is collected on the relevant case report forms. Continuous variables included in demographic, baseline, peri-operative and postoperative summaries, will be evaluated using descriptive statistics (N, mean, median, standard deviation, minimum, and maximum). Dichotomous and polychotomous variables included in demographic, baseline, peri-operative and postoperative summaries, will be described as frequencies and percentages at each level of the categorical variable.

#### IDE Study Arm

The primary effectiveness endpoint, the safety endpoint and all secondary endpoints including bleeding and the individual components of the composite safety endpoint, will each be summarized by counts, percentages, and the upper bounds of one-sided 95% exact binomial confidence intervals (CI).

Patient function and health-related quality-of-life will be similarly addressed by summarizing baseline, 6-week, 3-month, 6-month, and 12-month (if available) reported outcomes and change at each time point in the Knee Society Scores and SF-12 Health Survey Physical and Mental Health Composite Scores (PCS & MCS), using descriptive statistics including mean, standard deviation, median, minimum, and maximum. The ITT analysis set will be used in all safety analysis. Specific analyses may be repeated in a Per Protocol analysis set that requires completion of the index procedure and no clinically significant protocol violations.

Intraoperative and immediate postoperative complication rates will be similarly summarized using descriptive statistics.

In addition to the above analyses, key safety and effectiveness results will be stratified by certain baseline characteristics (investigational site, age, gender, and median value of Knee Society Score) to confirm that the safety and efficacy of the TSolution One™ Surgical System is consistent among different subgroups.

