Success/Failure Criteria	
The study success criterion is to simultaneously demonstrate that the malalignment rate is less than or equal to 0.16 (effectiveness endpoint) and that the composite safety event rate is less than 0.136 (safety endpoint) based on one-sided exact binomial tests with type 1 error rate equal to 0.05. A p-value <math>\leq 0.05</math> for both tests will indicate study success.

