**$H_0: \pi_{\text{composite}} \geq 0.076 + 0.06 = 0.136$**

**$H_A: \pi_{\text{composite}} < 0.076 + 0.06 = 0.136$**

A one-sided Fisher's exact test will be used to test the primary safety hypothesis that the composite safety event rate is larger than historical control (0.076) plus the non-inferiority margin of  $\delta=0.06$ . That is, the null hypothesis is that the investigational device event rate is 0.136 or larger and the alternative hypothesis is that this event is less than 0.136. Based on the Sponsor's expectation that the technology is associated with improved outcomes, it was assumed for the purpose of sample size determination that that composite safety event rate for patients undergoing primary TKA with femoral and tibial preparation by the TSolution One™ Surgical System is 20% smaller than control, or equal to 0.0608. A one-sided type 1 error of  $\alpha=0.05$  was

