**The total sample size to be enrolled is equal to 115 (103 plus 10% for possible loss-to-follow-up).**

It can be noted that with N=103, the number (%) of patients experiencing the primary composite safety event must be no larger than 8 (7.8%) in order to achieve the primary study success criterion. With 8 of 103 patients experiencing the event, the upper bound of the one-sided 95% exact binomial confidence interval will be 0.1358 which is less than 0.136, thereby permitting rejection of the inferiority hypothesis and a conclusion of no clinically significant increase in the incidence of the composite safety endpoint.

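### Section 9.3 says subgroup stratification will confirm consistent safety and efficacy, but with about 7 malaligned knees and 6 composite events expected, the design cannot support that conclusion

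*Combined protocol and SAP*

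**What the plan says.** The last paragraph on the IDE arm in Section 9.3 (Analysis Plan) states that "key safety and effectiveness results will be stratified by certain baseline characteristics (investigational site, age, gender, and median value of Knee Society Score) to confirm"; the conclusion to be confirmed is that safety and efficacy "is consistent among different subgroups". It gives no criterion for consistency, no estimate or test comparing subgroups, and no age cut-point. It does not call the analyses exploratory or descriptive. The statistics that Section 9.3 names for the binary endpoints are counts, percentages and one-sided 95% exact upper bounds, each computed within a single group.

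The sample size was set for the two pooled tests only. Section 9.2 gives the effectiveness power at N=103 "patients if the true malalignment rate is 0.07". Section 9.1 assumes a composite safety rate "20% smaller than control, or equal to 0.0608". Study success (Section 1, Success/Failure Criteria) is judged "based on one-sided exact binomial tests with type 1 error rate equal to 0.05" and does not refer to subgroups.

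**The concern.** To confirm consistency is to conclude that subgroup rates do not differ by an amount that matters. That takes a comparison between subgroups and enough events to rule out a material difference. The plan has no comparison, and its own planning rates imply very few events. Percentages that happen to look alike would then be read as confirmation, when the data could equally fit a severalfold difference. At stake is one secondary conclusion of the trial: that the pooled result applies evenly across sites, ages, sexes and baseline knee function.

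**Working it through.** **Inputs.** Malalignment: null rate 0.16, planning rate 0.07 (Section 9.2). Composite safety: null rate 0.136, planning rate 0.0608 (Section 9.1). N=103 for analysis, 115 enrolled. One-sided alpha 0.05 for the pooled tests.

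**1. The plan's own figures.** With exact binomial tests at N=103:
- Effectiveness: reject at 10 or fewer malaligned knees; exact alpha 0.0476; power 89.4% (stated 89.3%).
- Safety: reject at 8 or fewer events; exact alpha 0.0494; power 82.5% (stated 82.5%). The upper bound for 8/103 is 0.1358, as stated.

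So the pooled design reproduces.

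**2. Expected events.** 103 × 0.07 = 7.2 malaligned knees; 103 × 0.0608 = 6.3 composite events.

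**3. Power between two halves.** Assume a near-equal split of 51 and 52, as a median split of the Knee Society Score would give, with the overall rate p held at plan. For rate ratio R, the lower rate is p_L = 103p / (n_L + R·n_H) and the higher is p_H = R·p_L, where n_L and n_H are the sizes of the halves carrying them. Power is the sum of the two binomial probabilities, multiplied together, over all tables with two-sided Fisher p ≤ 0.05.

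| Endpoint | Ratio | Rates, approx. | Power, higher rate in the 52 | Power, higher rate in the 51 |
|---|---|---|---|---|
| Malalignment | 2 | 4.7% v 9.3% | 6% | 10% |
| Malalignment | 3 | 3.5% v 10.5% | 14% | 21% |
| Composite | 2 | 4.0% v 8.1% | 5% | 8% |
| Composite | 3 | 3.0% v 9.1% | 11% | 17% |

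The two columns differ because the test is discrete. For a 0 v 5 split, C(52,5)/C(103,5) = 0.0297 and C(51,5)/C(103,5) = 0.0268. With all five in the 52, the two-sided p adds both terms: 0.0565. With all five in the 51, it is 0.0268 alone.

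**4. Sensitivity, threefold difference.** Higher rate in the larger half, two-sided 5% unless stated.
- Pearson chi-square or normal approximation: 28% (malalignment) and 24–25% (composite).
- Split of 41 and 62: 15–21% and 11–18%, across Fisher and the normal approximation.
- Highest counts that still pass (10/103 and 8/103): 25–40% and 17–31%, across Fisher, Pearson and the normal approximation.
- Most favourable variant tried at the planning rates (57 v 58, one-sided, normal approximation): 43% and 39%.
- 80% power would need about 209 and 243 patients per stratum.

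**5. What agreement would look like.** Seven malaligned knees split 3/52 and 4/51 are 5.8% and 7.8%. The rate ratio is (4/51)/(3/52) = 1.36, with a 95% score interval of about 0.35 to 5.3. A split of 1/52 and 6/51, a ratio of 6.1, still has Fisher p = 0.06.

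**The case against.** The strongest reply is that this is one closing sentence, added to the main analyses. No test, sample size or success criterion depends on it. That stands: the point concerns interpretation only, and a reader who inferred that the primary conclusions are compromised would be wrong.

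It can also be said that the stratified results would naturally carry the same exact upper bounds as the pooled results, so imprecision within each subgroup would be visible. That is fair as far as it goes. A one-sided bound within each group still says nothing about the difference between groups, which is what consistency is about.

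Some stronger readings are tempting but lack support:
- A reader might infer that the sponsor intends a labelling claim of equal performance. The protocol says only that the evidence is to support a 510(k) submission (Section 3.4); no such claim is proposed.
- A reader might infer that a poorly performing site would be hidden. Rates by site would display it; the weakness lies in the conclusion drawn from them.
- A reader might fault the list for omitting baseline coronal deformity or surgeon case order. Deformity above 20° is an exclusion and baseline films are required, but the documents do not say that either item is recorded as an analysis variable. Omitting them is not an error.
- A reader might assume a median split for age. The word median applies only to the Knee Society Score.

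**Conclusion.** The point holds as one of interpretation. As written, Section 9.3 promises a conclusion that about 7 and 6 expected events cannot deliver. Power for a threefold difference between halves is roughly 14–21% (malalignment) and 11–17% (composite) by two-sided Fisher, and below 45% in every variant tried at the planning rates.

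This is low power, not impossibility: a 0 v 7 split with all seven in the half of 52 gives p = 0.013.

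The result rests on four assumptions: the planning rates hold; the strata are two near-equal halves; the overall rate stays at plan; and the key results, which Section 9.3 does not define, include the two primary endpoints. The number of sites is not given in the text reviewed. With more than two sites, at least some site strata would be smaller than the halves used here.

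**What to change.** In Section 9.3, change the stated purpose from confirming consistency to exploring whether safety and effectiveness differ across the listed characteristics. Add a sentence saying that similar subgroup rates, or a non-significant difference, will not be read as evidence of consistency. Report each subgroup rate with a two-sided exact 95% confidence interval, and each between-subgroup difference with its 95% confidence interval.

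This costs some wording and a few table columns, with no extra patients, visits or data. The sponsor gives up the claim of confirmation, and the intervals will be wide.

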#### Continued Access Study Arm

The continued access study arm will not include any hypothesis testing and will not be part of the primary or secondary endpoint analysis. Data from the continued access arm will be provided as

#### **THINK Surgical, Inc.**

Proprietary rights of THINK Surgical, Inc. are involved in the subject matter of this material. It is submitted in confidence for a specific purpose and the recipient by accepting this material agrees that it will not be used other than for the express purpose for which it was delivered.

Disclosure to others without written permission from THINK Surgical, Inc. is forbidden.

descriptive statistics, which can include counts, percentages, mean, standard deviation, median, minimum, and maximum and the upper bounds of one-sided 95% exact binomial confidence intervals (CI). This analysis will included safety, patient function, and health related quality-of-life described by summarizing baseline, 6 week, 3-month, 6-month, and 12-month (if available) scores, and change in scores from baseline at each time point, as applicable.

## 10. SAFETY REPORTING

### 10.1. Definitions

**Adverse Event** – An adverse event (AE) is any untoward medical occurrence, disease, injury, or untoward clinical signs (including abnormal laboratory findings, surgical complications, etc.), whether related or unrelated to the investigational device or its use.

**Adverse Device Effect** – This is an adverse event related to the use of an investigational device.

**Serious Adverse Event** – A Serious Adverse Event (SAE) is an adverse event which:

1. Led to a death,
2. Resulted in life threatening illness or injury\*
3. Resulted in patient hospitalization or prolongation of existing hospitalization,
4. Resulted in patient disability or permanent damage or required intervention to prevent permanent impairment/damage
5. Led to a congenital abnormality or birth defect

*\* NOTE: the term “life-threatening” refers to an event in which the patient was at a risk of death at the time of the event; it does not refer to an event which hypothetically might have caused death if it were more severe.*

**Unanticipated Adverse Device Effect (UADE)** – An Unanticipated Adverse Device Effect is:

1. Any serious adverse effect on health or safety or any life threatening problem or death caused by, or associated with, a device, if that effect, problem, or death is not identified in nature, severity, or degree of incidence in this protocol; or
2. Any other unanticipated serious problem associated with a device that relates to the rights, safety, or welfare of the patients.

### 10.2. Adverse Event Documentation

Adverse event collection will begin from the time of first incision. All medical events and conditions prior to this time point are to be captured as medical history.

Observed and reported adverse events shall be recorded in the patient’s study records and on the Adverse Event eCRF within 72 hours of the site becoming aware of each event, and must include the following information at minimum:

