**Table 1: Summary of Primary TKA Complications Assessed in the Primary Safety Endpoint**

Complications of Primary TKA (29)	Knee Society Definition (29)	Literature-Based Incidence Rate for Primary TKA	Method for Assessing Complications
1. Medial Collateral Ligament Injury	Intraoperative or early postoperative medial collateral ligament injury requiring repair, reconstruction, a change in prosthetic constraint, revision surgery, or TKA protocol	2.7% (30)	Incidence of intraoperative or postoperative MCL transection or avulsion leading to repair, reconstruction, change in prosthetic constraint, or revision TKA.
2. Extensor Mechanism Disruption	Disruption of the extensor mechanism (surgical repair and/or extensor lag should be recorded)	2.1% (31)	Incidence of iatrogenic extensor mechanism disruption.
3. Neural Deficit	Postoperative neural deficit (sensory or motor) related to the index TKA	1.3% (32)	Incidence of sensory or motor neural deficit (complete or incomplete) related to the TKA procedure.
4. Periprosthetic Fracture	Periprosthetic fracture of the distal femur, proximal tibia or patella (operative or nonoperative treatment should be recorded)	0.68% (32)	Incidence of periprosthetic fracture of the distal femur, proximal tibia or patella. Operative and nonoperative treatment for the fracture will also be recorded.
5. Patellofemoral Dislocation	Dislocation of the patella from the femoral trochlea (direction of instability should be recorded)	0.5% (33)	Incidence of patella dislocation from the femoral trochlea due to postoperative instability. The direction of instability will also be recorded.

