## 6.5. Study Enrollment

Each Investigator shall maintain a Screening & Enrollment Log for all primary TKA patients that are recruited for the clinical trial and screened for eligibility. This log will be used to document all patients who agree to be screened, including the ones that withdraw consent during the screening process or are determined not to meet the eligibility criteria. If a patient is excluded from the study, the reason for exclusion will be recorded on the log. Patients who meet the eligibility criteria and consent to participate shall be assigned a unique Subject Identification Number that will be captured on the Screening & Enrollment Log and used to identify them on all source documents and Case Report Forms thereafter. Patients will be considered to be enrolled once they have signed the Informed Consent Form and been assigned a Subject Identification Number. Enrolled patients that elect to withdraw consent prior to treatment with the investigational device will be considered screen failures under inclusion criteria (e).

Patients who do not meet eligibility criteria will have the primary reason for ineligibility captured in the study database on the Eligibility Criteria eCRF. No other CRFs will be completed for these patients.

Once enrollment is complete in the IDE Study Arm, subjects will be enrolled into the Continued Access Arm.

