### ***Preoperative CT for TCAT Planning***

A preoperative CT scan will be taken of the investigational knee for preoperative planning in TPLAN per the TSolution One IDE Study Radiographic Evaluation Protocol. A motion rod will be scanned with the joint to ensure that the patient did not move during the CT scan. If motion is detected during the scan, the scan will be repeated. This scan must be performed within 30 days prior to the date of surgery.

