### ***Anesthesia and Surgical Exposure***

## **THINK Surgical, Inc.**

Proprietary rights of THINK Surgical, Inc. are involved in the subject matter of this material. It is submitted in confidence for a specific purpose and the recipient by accepting this material agrees that it will not be used other than for the express purpose for which it was delivered.

Disclosure to others without written permission from THINK Surgical, Inc. is forbidden.

Once the diagnostic procedures have been successfully completed, the patient will be anesthetized. The Investigator will proceed with surgical exposure for the TCAT surgery in the same manner as a conventional TKA procedure.

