### ***Operative Summary***

During the immediate postoperative period, the Investigator's standard postoperative care procedures should be followed. Once the investigational procedure and all post-operative care has been completed, the Investigator will document procedure details in the source documents, including but not limited to the following:

- Surgery duration: measured via the surgery start time (start of anesthesia) and surgery stop time (dressing complete)
- Skin-to-skin time: measured via the time of first incision and time of completion of closure
- TCAT procedural time: measured via the time of insertion of bone motion recovery markers and time of removal of the TCAT system from the operating table
- Use of tourniquet, and estimated time of use

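### Events that occur and are recognised after the planning CT or the start of anaesthesia but before first incision become medical history, with no AE, SAE or UADE route

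*Combined protocol and SAP*

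**What the plan says.** Section 10.2 sets the window: "Adverse event collection will begin from the time of first incision". The next sentence disposes of everything before it: "All medical events and conditions prior to this time point are to be captured as medical history".

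Other sections show what has already happened to the patient by then:

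- Section 6.5: "Patients will be considered to be enrolled once they have signed the Informed Consent Form and been assigned a Subject Identification Number".
- Section 7.1: "A preoperative CT scan will be taken of the investigational knee for preoperative planning in TPLAN". The scan falls within 30 days before surgery. Section 3.2 says the system needs it, and Section 3.1 lists the added radiation among the system-specific risks.
- Section 7.2: "Once the diagnostic procedures have been successfully completed, the patient will be anesthetized". Surgical exposure comes after that.

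Two passages describe a wider safety window. Section 3.2 has subjects monitored for adverse events from Day 0, and the adverse-event definition in Section 10.1 carries no time limit. In Tables 2 and 3 the Safety Evaluation row begins at the Surgical Visit, and Medical History is marked only at Baseline.

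For the primary safety composite, the assessment method for the neural-deficit row of Table 1 is: "Incidence of sensory or motor neural deficit (complete or incomplete) related to the TKA procedure". The definition beside it speaks of a postoperative deficit. Neither mentions first incision.

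**The concern.** The rule sorts events by when they happen, and its cut-off falls after two exposures that the patient has because of the planned study procedure: the planning CT and the anaesthetic. A serious reaction at induction, or an operation given up between induction and incision, is something a safety review of the procedure would want to see. Under Section 10.2 it is a background condition.

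What is at stake is mainly the completeness of the safety record and the sponsor's oversight. SAE notification, UADE review and the termination decision all depend on events being reported. A lesser question is whether the same rule could affect the neural-deficit component of the primary safety composite.

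**Working it through.** **1. The interval, in time order**

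| Point in time | Source | Status of an event arising then |
|---|---|---|
| Consent and Subject ID (Baseline visit up to 90 days before surgery) | 6.5, 7.1 | Medical history |
| Planning CT (within 30 days before surgery) | 7.1 | Medical history |
| Start-up diagnostics, then anaesthesia | 7.2 | Medical history |
| First incision onward | 10.2 | Adverse event |

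The Day 0 window in Section 3.2 covers the hours on the day of surgery before incision, so it conflicts with Section 10.2 for anaesthesia. It does not reach back to a CT done on an earlier day. For the CT interval, the conflict is with the untimed definition in Section 10.1.

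**2. The reporting chain**

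- Section 10.1 defines an SAE as a kind of adverse event.
- Section 10.2 attaches severity, seriousness and relatedness to the Adverse Event eCRF.
- Section 10.5 triggers sponsor notification from entries on that form marked serious.
- Section 10.6 has the sponsor look for UADEs among the reported SAEs.
- Section 10.7 bases the termination decision on reported events.

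An event filed as medical history enters none of these steps. The UADE definition itself is not timed, but the review that would find a UADE works from reported SAEs. The fallback is also weak: with Medical History scheduled only at Baseline, an event on the day of surgery has no scheduled place even as history. If the patient then withdraws consent before device treatment, Section 6.5 makes them a screen failure, for whom it appears that only the Eligibility Criteria form is completed.

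**3. The composite: the plan's figure first**

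Inputs from Section 9.1: N = 103, null rate 0.076 + 0.06 = 0.136, assumed true rate 0.0608, one-sided alpha 0.05, exact binomial test. The limit c is the largest count with P(X ≤ c | 103, 0.136) ≤ 0.05.

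- P(X ≤ 8) = 0.0494 and P(X ≤ 9) = 0.0924, so c = 8.
- Power = P(X ≤ 8 | 103, 0.0608) = 0.8252. The plan states 82.5%.
- The one-sided 95% upper bound is the 0.95 quantile of Beta(k + 1, N − k). For k = 8 it is 0.1358, as the plan states. For k = 9 it is 0.1475.

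So 8 of 103 passes and 9 of 103 fails. (Section 5.2 gives a margin of 7.0% instead, a separate inconsistency. It would put the threshold at 0.076 + 0.07 = 0.146, and 0.1475 still fails.)

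**4. How much the composite could lose**

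The documents do not say what share of neural deficits would be dated before incision, so the share f is an assumption. With the 1.3% reference rate from Table 1, expected missed events are 103 × 0.013 × f. The chance of passing when the true composite rate is 0.136 becomes P(X ≤ 8 | 103, 0.136 − 0.013f).

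| f (assumed) | Expected missed events | Chance of passing at a true rate of 0.136 |
|---|---|---|
| 0 | 0 | 0.049 |
| 10% | 0.13 | 0.053 |
| 25% | 0.33 | 0.059 |
| 50% | 0.67 | 0.071 |
| 100% | 1.34 | 0.101 |

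The last row requires every neural deficit to be lost and is an outer limit, not a forecast.

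**The case against.** The device acts only after exposure, eligible patients need a knee replacement in any case, and six of the seven components in Table 1 are surgical or mechanical. Starting collection at incision is therefore a defensible choice for judging the device. The only CT harm the documents name is radiation, and a delayed effect appearing during follow-up would already fall inside the window. This is fair and limits the practical weight of the CT interval. It does not justify leaving a serious event at induction outside safety reporting, or the mismatch with Sections 3.2 and 10.1.

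Four stronger readings are tempting, and the documents do not support them.

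- **Anaesthetic harms are never reported.** The rule turns on timing, not cause. Harms that appear after incision are adverse events, and Sections 7.2 and 7.3 require intraoperative and postoperative complications to be documented.
- **Nerve injuries caused before incision are excluded from the composite.** Table 1 has no onset condition. In an anaesthetised patient such an injury would ordinarily be recognised after surgery and would count if judged related. To lose it, a site would have to date the deficit back before incision and then apply Section 10.2 in preference to Table 1. The documents do not state the type of anaesthesia either.
- **The narrow pass mark shows that this rule could decide the trial.** One event separates pass from fail for any counting question. That does not show that an event would be lost here.
- **The Operative Summary contradicts Section 10.2 by dating surgery from anaesthesia.** The phrase "surgery start time (start of anesthesia") defines a duration measure; the same list times first incision separately. It sets no safety window.

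**Conclusion.** The gap is a stated rule, not a missing detail. An event that occurs and is recognised after the planning CT or the start of anaesthesia, and before incision, has no AE, SAE or UADE route. That conclusion rests on the text alone. The documents give no rate for such events, so their number cannot be estimated.

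An effect on the primary safety composite is only a possible reading. It arises because nothing says whether cause, onset or detection decides, or whether anaesthesia counts as part of the TKA procedure. It would favour the device, but is probably near the low end of the range shown: about 0.13 missed events, and a chance of passing of 0.053 instead of 0.049, if 10% of neural deficits were lost. This assumes that the 1.3% reference rate applies to the device and that a patient whose deficit is lost has no other composite event. The case for changing Section 10.2 is safety capture, and it stands without the composite.

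**What to change.** 1. In Section 10.2, begin adverse-event collection at the first study-specific procedure after consent, named as the planning CT, and in any case no later than the start of anaesthesia.
2. In the same section, define medical history as events and conditions with onset before that same time point. Tying it to consent instead would leave events between consent and CT unclassified.
3. Mark Safety Evaluation in Tables 2 and 3 to match, with a Baseline entry for events from the CT onward, and bring the window in Section 3.2 into line.
4. Beside Table 1, state that a neural deficit first noted after surgery is assessed under the existing relatedness test and is not excluded because its onset is dated before incision. Do not count such deficits automatically: that would override the relatedness test and depart from the definition set beside the 1.3% reference.

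The cost is a few sentences, a schedule mark in each table and probably a few additional adverse-event records, including unrelated illness in the up to 30 days between CT and surgery. The reported event count may be slightly higher. The sample size and the test do not change.
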